### ***Study design***

This ITT, randomized, single-site trial uses a superiority design that compares active treatment to sham control. This trial will evaluate efficacy and safety endpoints during opioid discontinuation within an inpatient setting, and subsequent outpatient assessment of opioid and non-opioid substance use following discharge (primary and secondary endpoints, respectively). Fifty participants will be randomized to each of the two treatment arms (active and sham) and prospectively followed. **Figure 2** illustrates the study schema. **Figure 3** illustrates the schedule of activities.

As the platform for this trial, all participants receive treatment as usual (TAU), except MOUD, which they choose (as part of informed consent) not to receive as a condition of inclusion in this study. Participants could experience clinical deterioration during inpatient discontinuation of illicit opioids, prescribed opioid agonist medications (buprenorphine, methadone), and other illicit substances. Participants are instructed that device use (active or sham treatment) is self-administered, they may discontinue device use at any time and for any reason and can receive TAU for their clinical condition including MOUD and comfort medications.

The rationale for the minimum 1-hour device treatment period is to ensure a controlled degree of exposure to the device (active or sham) for all participants; based on prior open-label studies, the active device produces benefits in about 15-20 min. Completing this 1-hr period triggers study follow-up assessments. The rationale for the 7-day maximum device treatment period is to limit variability in the duration of exposure (to be treated as a covariate in analyses); as **Figure 1** indicates, the majority of participants stop active device use after about 7 days.

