The sham and active interventions both use the NET Device without alteration. The sham intervention uses lead wires that have been rendered non-conductive beforehand, preventing any electrical stimulation from being delivered to the participant. Before study initiation, the biostatistician allocated a random and unique Study Device Number (SDN) to each identical-looking active and sham lead wire, applying pre-printed SDN heat shrink. At the study site, the research assistant is notified electronically of participant inclusion, and selects a device and lead wires by SDN from a pre-printed randomization table for delivery of active or sham treatment. At the end of the study, all lead wires will be delivered to the biostatistician for verification against the group assignment by measuring conductivity using the sponsor-supplied validation circuit.

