## ***Statistical analysis plan***

Sample size determination. Sample size is based on statistical power analyses for the primary hypothesis based on single primary outcome (opioid abstinence without MOUD). A conservative approach was used to preserve power with a smaller effect size than observed from prior uncontrolled, non-blinded intervention studies with the NET Device. Power analyses examined sample sizes required to detect clinically meaningful group differences between sham and active groups. This represents standardized difference between the two groups after adjusting for the effect of the covariate “duration of inpatient residence” (which is capped at 28 days). Sample size determination was carried out *via* simulation in R-software; 5000 iterations were run in which group means were generated using a mixed-effect additive model. Sample size is a function of hypothesized effect size (standardized group difference) and the sign and magnitude of the regression coefficient (duration of inpatient residence). With projected N=100 (enrolled) there will be sufficient power to detect a standardized effect size of 0.45 or higher.

Missing data. In this ITT design, a participant is “included” (becomes part of the evaluable ITT data set) when he/she completes 1-hr of device use. We expect only 5% attrition, i.e. for 100 participants who complete 1-hr of device use, we expect to consent 105 individuals. A comparable trial of a

percutaneous electrical stimulation device for treating opioid withdrawal symptoms found that 71 of 73 enrolled participants completed 1-hr of device use, only 2.8% attrition [18]. **Table 1** explains how missing data are handled, i.e. for the primary efficacy endpoint, missing data are imputed as “not opioid abstinent without MOUD”. The definition of the primary endpoint (“opioid abstinence without MOUD”) and secondary endpoint (“non-opioid abstinence”) thus covers any intermittent missing values and loss to follow-up, and is not expected to impact power of the primary analysis. Premature study termination (e.g., death, relocation, or adverse events) may result in missing data, although this attrition is expected to be low. The projected sample size (N=125) was increased to cover unforeseen events.

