Participant withdrawal. Participants can withdraw from the study at any time on request. Discontinuation of device use prior to completing the minimum 1-hr treatment period constitutes withdrawal from the study. The investigator may discontinue or withdraw a participant from the study for the following reasons: (1) significant study intervention non-compliance; (2) if any clinical adverse event (AE), laboratory abnormality, or other medical condition or situation occurs such that continued participation in the study is not in the best interest of the participant; (3) disease progression which requires discontinuation of the study intervention; (4) if the participant meets an exclusion criterion (either newly developed or not previously recognized) that precludes further study participation; or (5) participant is unable to receive treatment following enrollment.

Participants who sign the informed consent form and are randomized but do not receive the study intervention will be replaced. Participants who sign the informed consent form, are randomized, receive the study intervention, and subsequently withdraw or are withdrawn, will be replaced.

Participants who withdraw from the study will receive TAU as defined by treatment staff (who are independent of the research staff), where such care may include MOUD.

Lost to follow-up. A participant is considered lost to follow-up if s/he becomes unavailable for all video assessments following discharge from the inpatient environment.

Populations for analysis. The ITT analysis dataset and the safety analysis dataset will contain all randomized participants. The per-protocol analysis dataset will contain the subset of the ITT dataset who: (1) present with a COWS score of moderate or above; (2) receive at least 1 hr treatment from the device; and (3) complete at least one post-discharge video interview.

Efficacy endpoints. The primary analysis will assume that data came from a mixed-effect linear model. Each model will include a random intercept, fixed effect for treatment, participant-specific random effect and covariate corresponding to duration of inpatient residence. The primary hypothesis involves testing the main effect for treatment difference between the groups (sham vs. active). A likelihood ratio test will examine the group effect focusing on the primary hypothesis.

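### The safety set is all randomized participants, so anyone who never wore the device dilutes device-event rates, and a conflicting one-hour rule could instead drop people who stopped early

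*Combined protocol and SAP*

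**What the plan says.** All places are in the combined protocol and SAP.

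- **Populations for analysis** (Statistical analysis plan): "The ITT analysis dataset and the safety analysis dataset will contain all randomized participants". The per-protocol set is the part of ITT that meets a withdrawal-score threshold, has at least one hour of treatment and has one post-discharge interview. ITT may therefore contain people without these.
- **Participant withdrawal**: "Participants who sign the informed consent form and are randomized but do not receive the study intervention will be replaced". Nothing says that the replaced person leaves the safety set. Stopping the device before one hour counts as withdrawal from the study.
- **Missing data**: a participant "becomes part of the evaluable ITT data set) when he/she completes 1-hr of device use". It continues: "We expect only 5% attrition, i.e. for 100 participants who complete 1-hr of device use, we expect to consent 105 individuals".
- **Outcome measures** and **Safety endpoints**: the safety endpoint is the prevalence of AEs, SAEs, ADEs, SADEs, UADEs and device deficiencies, summarized descriptively. No other denominator is given, and no rule for grouping participants by what they received.
- **Randomization and blinding**: lead wires are picked by Study Device Number from a printed table. At study end all are returned for "verification against the group assignment by measuring conductivity".

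**The concern.** A prevalence of device-related events is meant to describe people exposed to the device or its sham. A person who was randomized but never had the electrodes attached adds one to the denominator and can never add to the numerator for ADEs, SADEs, UADEs or device deficiencies. The error therefore runs in one direction, towards a safer-looking device. It matters more than usual because the planned safety analysis is only a descriptive table, and the Data & safety monitoring section states that the trial has no data safety monitoring board.

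The one-hour rule in the Missing data paragraph creates the opposite problem. The Populations paragraph ties ITT and safety to the same people in one sentence. An analyst who takes ITT from the Missing data paragraph and uses that set for both purposes would exclude everyone who wore the device for less than an hour. These are the people most likely to have stopped because of something they felt.

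**Working it through.** **1. Reproduce the plan's figure.** Inputs from Missing data: 100 people completing one hour, 5% attrition, 105 consented.
- 100 × (1 + 0.05) = 105, which matches.
- 100 / (1 − 0.05) = 105.26, or 106 rounded up, which is within one person.

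The 105 counts people consented, not randomized. The five lost can include people who were never randomized and people who wore the device for under an hour. Neither kind is randomized and unexposed, so treating all five as randomized and untreated gives an upper bound.

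**2. Dilution of device-event rates.** With no device events among the untreated:

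reported rate = true rate among exposed × (exposed / randomized)

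At 100 exposed of 105 the factor is 100/105 = 0.952, a relative understatement of 4.8%. The documents give no event rates, so the true rates below are assumptions.

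| Assumed true rate | Reported with 105 in the denominator |
|---|---|
| 2% | 1.90% |
| 5% | 4.76% |
| 10% | 9.52% |
| 20% | 19.05% |
| 50% | 47.62% |

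**3. The plan's external benchmark.** It cites "71 of 73 enrolled participants completed 1-hr of device use, only 2.8% attrition". 1 − 71/73 = 2.7% (the printed 2.8% is 2/71). At that rate an assumed 20% would read 0.20 × 71/73 = 19.5%.

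**4. Uneven split between arms.** The Study design section says "Fifty participants will be randomized to each of the two treatment arms". If all five untreated people fell in one arm that still had 50 exposed, that arm's factor would be 50/55 = 0.909, and an assumed 20% would read 18.2%. An even split leaves both arms at 0.952.

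**5. All-cause adverse events.** Untreated people discontinuing opioids can have adverse events. Let their rate be k times the exposed rate, with an assumed exposed rate of 20%:

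reported rate = (100 × 0.20 + 5 × k × 0.20) / 105

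- k = 0: 19.05%
- k = 0.5: 19.52%
- k = 1: 20.0%, no dilution

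The Study design section says that completing one hour triggers the follow-up assessments. Events in untreated people may therefore be under-recorded, which pushes the result towards the k = 0 end, but the documents do not settle this.

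**6. The two paragraphs side by side.**

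| Participant | Populations for analysis | One-hour rule, if applied to the shared set |
|---|---|---|
| Randomized, never wore the device | In; dilutes device-event rates | Out |
| Wore the device for under one hour | In | Out, with any event |
| Wore the device for one hour or more | In | In |

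Neither column is exactly the exposed population. The plan does not say how many of the five would be early stoppers, so the second column's loss cannot be sized.

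**The case against.** The strongest reply is that an all-randomized set loses no events, the summary is descriptive with no test to bias, and the number of people concerned may be close to zero. The last part has some force. Table 2 lists the withdrawal-score threshold as an inclusion criterion, and lead wires are selected once inclusion is notified. On that reading the main reason for non-treatment comes before allocation. The Schedule of Activities, whose table is broken in the text, appears to place randomization ahead of the baseline score, so the order is unclear. The plan still provides for randomized, untreated people, so its definition should cope with them.

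Three stronger readings are tempting, and the documents do not support them.

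- **A 20% relative understatement.** A reader might combine 100 exposed with "The projected sample size (N=125) was increased to cover unforeseen events" and find that a true 20% reads 0.20 × 100/125 = 16.0%. Nothing says that 25 people would be randomized and never wear the device. The allowance follows a mention of death, relocation and adverse events, and the plan also replaces people who were treated and then withdrew. Those people are exposed.
- **Understatement of all adverse event rates.** Step 5 of the working shows that this depends on the rate among the untreated and vanishes when that rate equals the exposed rate.
- **Safety grouped by assigned arm.** The plan says who is in the set, not how they are grouped. It is silent on as-assigned versus as-treated, and the conductivity check would reveal a mismatch. What is missing is a rule for using the result.

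**Conclusion.** The point holds for device-related events. The stated safety set includes people who cannot contribute to the numerator, and the bias favours the device. On the plan's own attrition it is small: at most about 4.8% relative with both arms pooled, or about one percentage point on an assumed 20% rate. That bound assumes that all five people lost before one hour were randomized and unexposed, and that they had no device events. For all-cause adverse events, dilution is possible but not established.

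The conflict over the one-hour rule is a separate reason to act. Its size cannot be estimated from the documents, but the people it would remove from the safety tables are those whose early stopping may itself be a safety signal. The correction is worth making for both reasons. Neither puts the primary efficacy analysis at risk through the safety tables.

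**What to change.** - Reconcile the Missing data and Populations for analysis paragraphs so that one definition of ITT stands, and keep it as all randomized participants.
- Define the safety set separately: every participant with any device application, active or sham, from the moment electrodes are attached and for any duration, including under one hour. Attachment is a better criterion than switch-on, which would drop a problem arising before stimulation begins.
- Summarize safety by the lead wire actually used, taken from the Study Device Number record. Use the conductivity check to confirm that record and review any discrepancy. The check should not decide the group alone, because it is made at study end and an active wire that failed after use could be mistaken for a sham one.
- List events in randomized but untreated participants separately, so that none is lost.

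The cost is a few sentences in the SAP. Device-event rates become slightly less favourable: at the upper bound, a reported 19.05% becomes 20% and a reported 4.76% becomes 5%.

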During a given week, oral fluid samples and self/pharmacy reports that both indicate no illicit opioid, methadone, buprenorphine, or naltrexone use will be considered "opioid-abstinence without MOUD". Cumulative distribution function, time (days) to first use of illicit opioids, time (days) to first use of MOUD, and duration (weeks) of continuous abstinence without MOUD will be evaluated as supportive outcomes. Response profiles for each treatment arm are based on each participant's individual rates of weekly illicit opioid or MOUD use, including negative oral fluid results and daily

self (TLFB) of illicit opioid or MOUD use/non-use. **Table 1** presents explanatory cases of the primary efficacy endpoint measurement. The null hypothesis is that “opioid abstinence without MOUD” will not significantly differ between active and sham groups, whereas the alternative hypothesis is that “opioid abstinence without MOUD” will be superior in the active (relative to sham) treatment arm.

The secondary efficacy endpoint is each participant’s percentage of non-opioid drug-free weeks during the 12-week outpatient period. Non-opioids assessed include cocaine, sedatives, and stimulants. Use of alcohol and cannabis will be measured, but are not included in the secondary efficacy analysis, due to their legal status. Response profiles for each arm are based on each participant’s individual rates of weekly abstinence data, including negative oral fluid results and daily self-reports of non-opioid drug use/non-use (TLFB).

The secondary safety endpoint is the prevalence of all adverse events (AEs), serious adverse events (SAEs), adverse device effects (ADEs), serious adverse device effects (SADEs), unanticipated adverse device effects (UADEs), and device deficiencies.

Supportive and exploratory measures. Treatment retention will be measured throughout the inpatient and outpatient phases. Self-stimulation intensity (in 5-min bins), duration, and device on/off data from each NET Device are automatically transmitted to a computer server and processed offline. Opioid withdrawal symptoms, craving severity, and positive/negative affect are measured daily during the first inpatient week. Measures of depression, anxiety and stress, sleepiness, and health-related quality of life are obtained at the conclusion of inpatient and outpatient phases.

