Secondary endpoint analyses are not powered, but may be used to demonstrate additional benefits of the treatment, provided it has been demonstrated that the primary endpoint shows clear statistical significance, as well as clinical meaningful benefits of the treatment [19]. Analysis of the secondary endpoint resembles primary endpoint analysis, using mixed-effect model testing for the between-group main effect.

Given that participants can control the level of device stimulation, exploratory regression analyses will seek to identify potential relationships between device utilization (e.g. number of minutes device ‘on’ [non-zero intensity], average intensity while device ‘on’) and efficacy endpoints.

Expected outcomes. We selected a single primary outcome (abstinence without MOUD). From our past experience at this same treatment facility, the expected group means for sham and NET arms are 0.48 and 3.97 weeks of average opioid abstinence with standard deviations 1.19 and 3.46, respectively. This results in effect size of 1.12. This effect size based on pilot data is rather large,

which is often the case due to limited scope of the pilot study. Thus, we took a conservative approach as suggested by Kraemer et al. [20] with moderate effect size of 0.45.

Safety endpoints. Secondary safety endpoints (AEs, SAEs, ADEs, SADEs, UADEs and device deficiencies) will be summarized using descriptive statistics.

Subgroup analysis. The analysis will stratify by sex (male/female) and non-opioid SUD (presence/absence). The expected outcome is that allocation on those variables will be balanced between the two groups. It is not anticipated that the primary outcome (opioid abstinence without MOUD) will differ across these subgroups. If significant baseline group imbalance is detected on any variable and its correlation with outcome ( $\geq 0.30$ ), that variable will be included as a covariate in the inferential analyses. If systematic variation is noted by any subgroups for primary or secondary outcomes, further exploration will be conducted via cluster analysis.

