**Figure 3. Schedule of Activities**

Schedule of Activities (SoA)	Pre-Screening	Screening	Inpatient					Outpatient	
			Week -1	Week 1			Weeks 2-3	Week 4	Weeks 5-15 Week 16
Inpatient Study Day(s)		Day 1	Day 1, Baseline	Day 1, One Hour Elapsed	Days 2-7	Day 14 Day 21	Day 28 (Discharge from Site)		
Outpatient Test Weeks								OP Wk 1-11 each Day 7	OP Wk 12 Day 7
Study Site Admission		X							
Study Site Discharge							X		
End of Study									X
Informed Consent	X	X 							
Demographics		X							
Medical and Psychiatric History		MIA 							
Drug Use History		MIA 							
Physical Exam (including height and weight)		MIA 							
Vital Signs (BP, HR, RR, O2)		MIA 							
Drug Screen		MIA 					X	X	X
Contraception, Pregnancy Test, Menstrual Cycle	X						X	X	X
Drug Use Timeline Followback Interview (TLFB)								X	X
Eligibility (Inclusion/Exclusion)	X								
Contact Data	X						X		
Randomization and Stratification	X								
COWS			X 	X	X				
Administer Active/Sham Treatment (self-administration [sa])			X	sa	sa				
Opioid Craving Scale (OCS)			X	X	X	X	X	X	X
Treatment Perception (while device in use [sa])				X	sa				
Device Satisfaction Scale (while device in use [sa])				X	sa				
Device Tolerability (while device in use [sa])				X	sa				
Dass21: Depression, Anxiety and Stress			X				X		X
PANAS-SF: Positive and Negative Affect Scale (Short Form)			X	X	X				
Epworth Sleepiness Scale			X				X		X
Concomitant Medications				X	X	X	X	X	X
Adverse Events			X	X	X	X	X	X	X
Device Deficiencies				X	sa				
SF-12 Health Related Quality of Life (Short Form)							X		X

This drug screen is wider ranging to collect stratification information

Must be >13 for inclusion on Day 1

Paper (non-electronic) source data

"MIA" is Study Site Medical Intake Assessment

Notes: "OP", outpatient. "Wk", week. "sa", self-administered. "BP", blood pressure. "COWS", Clinical Opiate Withdrawal Scale, "HR", heart rate. "RR", respiration rate. "O2", oxygen saturation.

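### The primary test adjusts for length of inpatient stay, which is known only after randomisation and device treatment, so it need not estimate the ITT difference

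*Combined protocol and SAP*

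**What the plan says.** The Study design section sets the objective: "This ITT, randomized, single-site trial uses a superiority design that compares active treatment to sham control".

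Under Efficacy endpoints, the SAP describes the primary model: "Each model will include a random intercept, fixed effect for treatment, participant-specific random effect and covariate corresponding to duration of inpatient residence". What is tested is the treatment main effect in that model, examined by a likelihood ratio test. For the secondary efficacy endpoint the SAP says "Analysis of the secondary endpoint resembles primary endpoint analysis". It does not name the covariate again, so its use there is an inference from that phrase and from the words that open the sentence on the primary model.

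Under Sample size determination, the powered effect is already an adjusted one: "This represents standardized difference between the two groups after adjusting for the effect of the covariate", the covariate being length of inpatient stay, capped at 28 days. The sample size is said to depend on the hypothesised effect and on "the sign and magnitude of the regression coefficient (duration of inpatient residence". No value is given for that coefficient.

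The Schedule of Activities starts device treatment on inpatient Day 1 and places the end of the stay at "Day 28 (Discharge from Site".

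Three other places come near the issue without settling it. Under Outcome measures, "Treatment retention will be measured throughout the inpatient and outpatient phases", but no comparison between arms is named. The covariate rule under Subgroup analysis begins "If significant baseline group imbalance is detected on any variable", so it concerns baseline variables only. The supportive outcomes (such as time to first use) carry no stated stay term, but they are not tests of the primary endpoint.

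**The concern.** Stay ends after randomisation and after device use, so it may itself respond to treatment. The protocol makes this plausible, although it does not show it: the device description says this type of stimulation can reduce the severity of withdrawal, and Study design says participants may deteriorate while discontinuing opioids as inpatients. Stay need not cause abstinence for the problem to arise. A shared cause of early discharge and relapse is enough to give a non-zero slope, and the power section itself allows for one.

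If both links exist, the test compares the arms at equal length of stay. That is a different quantity from the randomised difference on which an ITT superiority claim rests. With a positive slope:

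- if active lengthens stay, the ITT benefit is under-estimated, and false rejections when that benefit is zero favour sham;
- if active shortens stay, the errors favour active.

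A negative slope reverses both.

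**Working it through.** **The plan's own figure.** The SAP says N=100 gives sufficient power for a standardised effect of 0.45, but states no power, alpha, sidedness or stay coefficient. At an assumed two-sided 5%, 50 per arm and no covariate, the standard error is sqrt(2/50) = 0.200 and the noncentral t (98 df) gives 61%. Whether that counts as sufficient cannot be confirmed or refuted from the text.

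**Inputs.** From the documents: 50 per arm, 1:1 allocation and an effect of 0.45. Assumed, because the plan does not give them: two-sided 5%; the shift in mean stay on active, *s*, in within-arm SD units; and the within-arm stay-outcome correlation, *r*, taken as 0.3 unless stated.

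**Model.** One summary value per participant, within-arm SDs of 1, and T = 1 for active:

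- stay = s·T + e1
- outcome = total·T + r·e1 + sqrt(1 − r²)·e2
- adjusted coefficient = total − r·s
- SE (adjusted) = sqrt[(1 − r²)(2/50)(1 + s²/4)], 97 df

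The adjusted and total effects agree only if r = 0 or s = 0. The same identity was checked in a 12-week random-intercept mixed model on simulated data. The adjusted coefficient was 0.0909, the same as from least squares on participant means. The unadjusted difference was 0.1000, and adjusted coefficient plus slope × shift gave 0.1000.

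**A. 0.45 SD taken as the randomised effect.** Unadjusted power is 61% throughout. Example at s = +0.3: 0.45 − 0.3 × 0.3 = 0.36; SE = sqrt(0.91 × 0.04 × 1.0225) = 0.193; power 45.5%.

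| Shift on active (SD) | Adjusted estimate | Power of planned test |
|---|---|---|
| −0.3 | 0.54 | 79% |
| 0 | 0.45 | 65% |
| +0.1 | 0.42 | 59% |
| +0.3 | 0.36 | 46% |
| +0.5 | 0.30 | 33% |

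At s = +0.3, varying r from 0.1 to 0.5 moves the estimate from 0.42 to 0.30 and the power from 54% to 40%.

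**B. 0.45 SD taken as the adjusted effect, as the sample size section defines it.** The randomised difference is then 0.45 + r·s.

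| Shift on active (SD) | Randomised difference | Power, planned test | Power, unadjusted test |
|---|---|---|---|
| −0.5 | 0.30 | 62% | 32% |
| −0.3 | 0.36 | 64% | 43% |
| 0 | 0.45 | 65% | 61% |
| +0.3 | 0.54 | 64% | 76% |
| +0.5 | 0.60 | 62% | 84% |

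The planned test keeps its power, but the same adjusted effect is compatible with randomised differences from 0.30 to 0.60 SD.

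**C. Randomised effect of zero.** The nominal rate is 2.5% per side. False rejections on the affected side are 3.6%, 6.7% and 11.4% at shifts of 0.1, 0.3 and 0.5 SD. At 0.5 SD they range from 4.3% (r = 0.1) to 28% (r = 0.5). With these positive correlations, the affected side is sham if active lengthens stay and active if it shortens stay.

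**Checks.** Simulation with 40,000 replicates per scenario agreed within 1 point. Replacing the t cut-off by the likelihood ratio chi-square cut-off adds about 1 point of power (65.9% against 64.6% at no shift) and gives 5.4% two-sided error at no shift, so the pattern is unchanged.

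**The case against.** The strongest reply is that the plan is prespecified and consistent: it powers a stay-adjusted difference and tests that same difference. This is true, and reading B shows that the planned test loses almost no power on its own definition. It does not make that difference the randomised comparison, which is the comparison an ITT superiority claim implies.

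The size of any bias is also unknown. The documents give neither the slope nor the shift, nor how much stay varies below the cap. If most participants reach Day 28, an SD shift has a different meaning from the one in the unbounded normal model used here. The route from arm to stay is not strong: device use is limited to 7 days, and nothing links withdrawal relief to discharge date. If active lengthens stay and the slope is positive, the planned test is conservative for the superiority claim. The 28% figure needs the largest shift and the largest correlation together. All of this stands. It limits the finding to a conditional one but does not remove it.

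A possible motive for the covariate is that the 12-week outcome period starts at discharge, so participants are observed at different times since treatment. The plan does not give this reason. Removing the term would still leave an outcome period that starts at a post-randomisation event.

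Finally, 0.45 may be standardised by the residual SD. On that reading, with no shift, the planned test has 61% power. The unadjusted test has 57% at r = 0.3 and 49% at r = 0.5, so the fix costs more than reading B suggests.

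**Conclusion.** The concern holds. The mismatch between the tested coefficient and the ITT difference is certain as a matter of algebra in the planned additive linear model, unless arm leaves stay unchanged or the arm-adjusted slope is zero. The plan states neither condition and includes no analysis that would reveal a departure.

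Whether bias will occur, and in which direction, cannot be known from the documents. Every figure above rests on assumed alpha, shift and correlation. Small shifts matter little (3.6% against 2.5% at 0.1 SD); moderate ones could change the conclusion of the trial. The fault is in which effect is tested, not in the power of the planned test for the effect it defines. It should be corrected before the analysis. The extension to the secondary endpoint depends on reading its analysis as using the same covariate.

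**What to change.** 1. Base the primary and secondary treatment tests on a model with baseline covariates only: the two stratification factors, sex and non-opioid substance use disorder. The SAP already says the analysis will stratify by these.
2. Report length of inpatient stay by arm.
3. Keep the stay-adjusted model as a labelled sensitivity analysis that does not support the superiority claim.
4. Re-run the power simulation without the stay term. State alpha and sidedness, and say whether 0.45 is the randomised or the stay-adjusted difference and which SD standardises it.

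This needs SAP wording and a re-run of an existing simulation. It needs no new data, since stay must be recorded for the planned model anyway.

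There is a cost in power if stay is prognostic and unaffected by arm. With 0.45 in total-SD units, power falls from about 65% to 61% (r = 0.3) or from 73% to 61% (r = 0.5). In residual-SD units it falls from 61% to 57% or 49%. If 0.45 is the adjusted effect and active shortens stay by 0.3 SD, the ITT test has 43% against 64% for the planned test (39% against 60% in residual-SD units), because the randomised difference really is smaller. These figures are for a model with no covariates; any precision gained from the stratification factors was not evaluated.
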